4.3 Study Enrollment Procedures

We will not be enrolling clinicians. We are approved for a waiver of consent.

5.

STUDY INTERVENTIONS

5.1 Interventions, Administration, and Duration

The intervention period will be 34 weeks in length for all participants.

5.2 Handling of Study Interventions

The following interventions will be tested: *Accountable Justification (AJ)* is an EHR-based intervention that will prompt the clinician to justify, in a free text response, the decision to prescribe an opioid or to not reduce high risk/high dose prescribing. The prompt is designed to inform the clinician that the justification will be seen by others in the patient's medical record as an "High risk prescribing justification" note, and that if no justification is entered, the phrase "no justification given" will appear in the note.

Delivery of AJ nudges in Epic's electronic health record (EHR) based on patient type is described below.

Opioid-naïve: An automated search of EHR data determines whether the patient received an opioid prescription within 90 days. If no opioid was prescribed, the clinician receives an alert cautioning against initiating a prescription based on current guidelines. The clinician can either remove or continue with the current opioid prescription. The former results in return to normal workflow after receiving a prompt recommending physical therapy and non-opioid alternatives. The latter, however, induces a prompt requiring the clinician to justify their decision in free text. A Justification Note with the clinician's response is recorded in the Visit Summary portion of the patient's record. A generic "No justification given" is generated for blank responses.

At-risk for long term use: If an automated search of EHR data reveals an opioid prescription(s) within 90 days of the current order, but no previous opioid prescription prior to 90 days before, a prompt explaining the danger of continuing refills based on current guidelines appears. The process is otherwise the same as above; clinicians who cancel a prescription receive a prompt recommending non-opioid alternatives and physical therapy, whereas those who continue with the order are required to justify their decision.

Long term opioid recipient: If an automated search of EHR data reveals total opioid doses are at least 50 MME per day, there are two or more prior opioid prescriptions with two different start dates both greater than 1 day and less than 91 days, and there is a prior opioid prescription with a start date greater than 90 days and less than 181 days, a prompt suggesting an opioid taper appears.

5.3 Adherence Assessment

In order to ensure that the study interventions are being reliably delivered we will create testing scripts that cover logical and coding

variation in EHR-based interventions. Study staff will conduct best practice alerts reports during the intervention to ensure that tests do not fail.

6. STUDY PROCEDURES

6.1 Schedule of Evaluations

Assessment	Screening: Baseline prescribing	Baseline, Enrollment,	Intervention start (Month 1)	Continuously Measured or monitored	Intervention end: (Month 6)
Clinician-level Assessments					
Demographics	X				
Inclusion/Exclusion Criteria	X	X			
Visit-level assessments					
ICD-10 codes	X	X	X	X	X
Ordering Data	X	X	X	X	X
Adverse Events			X	X	X

6.2 Description of Evaluations

6.2.1 Screening Evaluation

Consenting Procedure

The study investigators will seek a waiver of consent.

6.2.2 Enrollment, Baseline, and/or Randomization

Enrollment

Eligible clinicians from one pilot clinic will receive study interventions.

Baseline Assessments

None

Randomization

None

7. SAFETY ASSESSMENTS

Data for patients who were noted to have been abruptly stopped of opioid prescriptions, emergency room eligible study visit with a diagnosis that could represent a serious complication of untreated pain will be extracted from study site EHRs and reported to the Data Safety and Monitoring Board. Relative rate of ED visits between study conditions will also be evaluated.

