2.1 Background on Condition, Disease, or Other Primary Study Focus

Over the last two decades, prescription opioids have grown to become a public health crisis. Today, on average 1 in 5 persons with chronic noncancer pain receives an opioid prescription in the U.S.¹ Yet, despite this record level of prescribing, reports of pain in America have not gone down.^{10,11} The greater availability of prescription opioids has been accompanied by alarming rise in the negative consequences related to their use. In 2015, there were over 365,000 emergency department visits for misuse and 20,101 prescription overdose deaths, more than have ever been recorded in U.S. history.⁵ The costs of prescription opioids are staggering. Aggregate costs for prescription opioid harms are estimated at over \$78.5 billion (in 2013 dollars). One-fourth of the aggregate economic burden is publicly funded (i.e., Medicaid, Medicare, and veterans' programs).^{12,13}

In 2016, the CDC issued the “CDC Guideline for Prescribing Opioids for Chronic Pain” which gives 12 patient care recommendations: (1) *use alternatives to opioids*, (2) *set realistic goals* for pain and function, (3) *discuss opioid risks* upon therapy initiation, (4) *use immediate release agents* instead of long-acting ones, (5) *use lowest effective starting dose, avoid escalation* above 50 milligram (mg) morphine equivalent (ME) daily dose and abide by a 90 mg ME/day dose prescribing limit, (6) *prescribe lowest dose at lowest quantity needed for acute pain*—usually 3 days with a maximum of 7 days in rare cases, (7) *evaluate for and discuss tapering* within 1 - 4 weeks and after 90 days, (8) *prescribe naloxone and evaluate substance use history* with opioid prescription, (9) *review the state prescription drug monitoring program data* (10) *conduct urine drug tests* to provide information about drug use that is not reported by the patient, (11) *avoid co-prescribing* with benzodiazepines, and (12) *refer patients with opioid use disorder to medication-assisted treatment in combination with behavioral therapies*. Our objective is to increase adherence to the CDC guideline and Oregon Pain Guidance pain management guideline. To evaluate the effects of doing so, we will measure as a primary outcomes clinician aggregate monthly mg ME

for patient visits with ≥ 50 mg ME daily dose. Secondary outcome is rate of dose escalation to ≥ 50 mg ME/day.

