7.3 Adverse Events

Per CDC guideline clarification, adverse events are defined as an abrupt discontinuation of opioids for persons whose most recent prescription exceeds > 49 morphine equivalent daily dose; or as reported to study staff. ([Dowell et al. 2019](#)) Emergency department visits will also be evaluated as well as *increases* in prescribing $> 20\%$ presumably in response to reports of worsening pain.

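### Emergency visits for overdose, withdrawal and self-harm are not separated by cause in the safety plan, and deaths reach the DSMB only by passive reporting

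*Combined protocol and SAP*

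**What the plan says.** Section 7 names two kinds of data for the DSMB: patients whose opioid prescriptions were abruptly stopped, and emergency visits with "a diagnosis that could represent a serious complication of untreated pain". These data "will be extracted from study site EHRs and reported to the Data Safety and Monitoring Board". The next sentence adds: "Relative rate of ED visits between study conditions will also be evaluated". Section 7.3 repeats the idea without a diagnosis limit: "Emergency department visits will also be evaluated".

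The other safety provisions are these:

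- Section 7.1 has dose changes of more than 20% in high-dose patients reviewed to see whether the drop was unsafe.
- Section 7.3 says that "adverse events are defined as an abrupt discontinuation of opioids for persons whose most recent prescription exceeds" a morphine-equivalent daily dose of 49, "or as reported to study staff". It also covers dose increases of more than 20%.
- Section 7.4 has the principal investigator report unanticipated events to the IRB and the DSMB.
- Section 7.2 says that reports on the safety measures go to the DSMB.
- The schedule in section 6.1 marks adverse events from intervention start onward, not at screening or baseline.

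Overdose and death appear only in the background, section 2.1, which cites "over 365,000 emergency department visits for misuse and 20,101 prescription overdose deaths" as national figures for 2015.

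**The concern.** The prompts in section 5.2 discourage starting or continuing an opioid, and suggest a taper for long-term recipients. Harm after a stop or cut need not present as pain. It may present as overdose, withdrawal or self-harm, or as a death with no emergency visit. The plan sets out one of these routes by diagnosis and leaves the others inside an overall count, or outside any active search.

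The DSMB may recommend stopping the study on safety grounds (section 9.3), but it can judge only what it is shown. With a single overall emergency-visit rate, a small rise in overdose or withdrawal visits could be hidden by the volume of unrelated visits or offset by a fall in another cause. The study runs under a waiver of consent (section 4.3) and is meant to inform a later cluster randomized trial (Précis). A safety extract that cannot separate these causes would also leave that trial without baseline information on them.

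**Working it through.** No arithmetic applies: the documents give no safety event rate, and section 9.2 gives no sample size calculation. The check is a reading of every safety section (6.1, 7 to 7.5, 9.3) and the data collection, management and quality sections (11.1 to 11.3.3), asking by which route each kind of event would reach the DSMB.

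| Event in a patient with an eligible order | Diagnosis-specific extract (7) | Overall emergency-visit rate (7, 7.3) | Report to staff or as unanticipated event (7.3, 7.4) |
|---|---|---|---|
| Emergency visit, serious pain complication | Yes | Counted | If reported |
| Emergency visit, overdose or poisoning | Not named | Counted, cause not shown | If reported |
| Emergency visit, opioid withdrawal | Not named | Counted, cause not shown | If reported |
| Emergency visit, self-harm | Not named | Counted, cause not shown | If reported |
| Admission without an emergency visit | No | No | If reported |
| Death without an emergency visit | No | No | If reported |

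Counted means counted if the visit is in the study-site EHR, the only source that section 7 names.

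The tally is:

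- one diagnosis-specific emergency category;
- two statements that evaluate emergency visits with no diagnosis filter;
- no safety measure that names overdose, withdrawal or self-harm;
- no measure of death and no source for it.

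Three features limit what the overall rate can show.

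1. **Link to the exposure.** Neither unfiltered statement ties a visit to a preceding stop or cut. Section 7.1 reviews the size of a dose change but names no patient outcome after it. The main adverse event definition in section 7.3 is likewise a prescribing event.
2. **Comparator.** Section 7 promises a rate between study conditions, but sections 6.2.2 and 9.2 describe one clinic and no randomization. The natural comparator is the 34-week baseline period (section 3). The plan does not say so, and section 6.1 schedules no adverse event capture before intervention start.
3. **Wording of the extract.** The sentence in section 7 is grammatically broken. It may describe two extracts (abrupt stops; emergency visits with the diagnosis) or one combined condition. On the first reading the pain visits are not tied to a stop. On the second they are, but pain visits after anything short of an abrupt stop drop out. Under either reading the other causes are not named.

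**The case against.** The strongest reply is that emergency visits are monitored without a diagnosis filter in two places, and section 7.2 makes it plausible that the overall result reaches the DSMB. That stands. A reader might infer from the pain wording that all emergency-visit monitoring is confined to untreated pain. The documents do not support this, since overdose, withdrawal and self-harm visits in the site EHR would enter the overall rate. What the reply does not supply is cause, link to a stop or cut, comparator, or deaths.

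Second, no code list for the pain category appears in the text, and its wording is broad. It cannot be shown that self-harm, for example, falls outside it. That also stands, so the supportable claim is that these causes are not distinguished, not that they are excluded.

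Third, a reader might take the DSMB to be the sole protection. It is not: section 7.1 requires close review of large dose changes, section 7.4 sends unanticipated events to the IRB as well, and section 12.1 records IRB review. A known overdose or death does have a reporting route, but no section says how such an event would be found.

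Fourth, the figures in section 2.1 describe national harms from opioid use, not harms from stopping. They show that the protocol regards overdose and death as serious, but do not make the safety plan contradict itself.

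Finally, this is a feasibility pilot with 41 clinicians, and finer tabulation will yield small counts. That is true, but small counts by cause are what a board can review case by case.

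**Conclusion.** The point holds in this form: the safety plan identifies one cause of emergency visit, untreated pain, and evaluates the rest only in aggregate. Overdose, withdrawal and self-harm are not distinguished or tied to a stop or cut, and deaths depend on passive reporting.

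Its size cannot be put in numbers. Any percentage of events missed would only restate an assumed share of visits by cause, and the unfiltered rate would in any case count those visits. The conclusion rests on the text as supplied; the linked code lists were not available. If they already group emergency diagnoses by cause, part of the point falls away, but the lack of a mortality measure and of a defined comparator would remain.

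This does not affect the primary analysis. It is a low-cost improvement to patient safety monitoring.

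**What to change.** In sections 7 and 7.3:

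- Extract all emergency visits and admissions, and all deaths recorded in the study-site EHR, for patients with an eligible opioid order. Say whether an order removed at the prompt counts as eligible, because the baseline period has no prompt and so no matching record.
- Tabulate them for the DSMB in fixed groups with a prespecified code list: overdose or poisoning, opioid withdrawal, self-harm, pain-related, other. Show deaths separately.
- Give counts and patient denominators for the 34-week baseline and the 34-week intervention period, and name baseline as the comparator in place of the reference to study conditions. Extend the adverse event row in section 6.1 to baseline.
- Flag each event that follows a stop or a dose change of more than 20%, the threshold that section 7.1 already uses, and state the time window.
- State that visits and deaths outside the site EHR may be missed, so a zero count is not evidence of no deaths.

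The cost is a longer diagnosis-code list, a vital-status field in the same extract, and more unrelated background events for the board to read. ICD-10 codes are already scheduled at every time point in section 6.1, though for visit-level assessments, so the programming should confirm that emergency and inpatient encounters are included. The before-and-after table would support monitoring only; without a concurrent control it could not attribute a change to the prompts.

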7.1 Specification of Safety Parameters

Data elements from qualifying visits for providers enrolled in the study will be collected from the electronic health record. Clinics will incorporate exclusions (ICD 10 cancer suppressor codes found [here](#)) used in the decision to trigger the clinical decision support. Aggregate counts of total visits across sites for which the intervention was triggered, for high dose opioid patients, if abrupt changes to dose ($> 20\%$ morphine equivalent daily dose) were made. Such cases will be examined closely to determine if unsafe drops in opioids occurred.

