1.1 Primary Objective

The objective of the R21 pilot phase of the Application of Economics & Social psychology to improve Opioid Prescribing Safety (AESOPS) study is to develop and test novel behavioral nudges to encourage adherence to pain and CDC guidelines for opioid prescribing for persons with noncancer pain. At the time of opioid prescribing, clinicians will be prompted with an EHR nudge when the prescribing history for the patient falls into one of the following three mutually exclusive categories: Opioid naïve, At-risk for long term use, or Long-term opioid recipient. The primary outcome is average weekly morphine milligram equivalents (MME) prescribed per-clinician.

2. **BACKGROUND AND RATIONALE**

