9.1 General Design Issues

Hypotheses

Our primary hypothesis is that clinicians receiving behavioral economic interventions will have lower opioid prescribing rates post-intervention as compared to baseline. We will estimate weekly milligram morphine equivalent for each clinician and observe the change each month. This will capture CDC guideline prescribing endpoints.

Design

The Application of Economics & Social psychology to improve Opioid Prescribing Safety (AESOPS) R21 is a pilot study to test the feasibility of clinical decision support nudges within the electronic health record to discourage unnecessary opioid prescribing through the application of "behavioral insights"— empirically-tested social and psychological interventions that affect choice. Over a 34 week study period, participating clinicians will receive any of three nudges when eligibility criteria are met within a patient's chart: 1) **Opioid naïve**: Visit where the order is for an included opioid and there is no prior opioid prescription with a start date of greater than 1 day and less than 91 days, 2) **At-risk for long term use**: Visit where the order is for an included opioid there is a prior opioid prescription with a start date greater than 1 day and less than 91 days, and there is no prior opioid prescription with a start date greater than 90 days, and 3) **Long-term opioid recipient**: Total opioid doses are at least 50 MME per day, there are two or more prior opioid prescriptions with two different start dates both greater than 1 day and less than 91 days, and there is a prior opioid prescription with a start date greater than 90 days and less than 181 days.

Outcome Measures

The primary outcome is change in weekly milligram morphine equivalent from baseline to post intervention period. We will estimate weekly milligram morphine equivalent for each clinician and observe the change each month. This will capture CDC guideline prescribing endpoints.

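### The section 7.1 dose-change count is tied to visits where the nudge fired, so it cannot include high-dose patients stopped without an opioid order, without a visit, or outside the three nudge categories

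*Combined protocol and SAP*

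**What the plan says.** Section 7.1 begins broadly, with collection of "Data elements from qualifying visits for providers enrolled in the study", although it does not define a qualifying visit. It then describes the tabulation: "Aggregate counts of total visits across sites for which the intervention was triggered, for high dose opioid patients", with a check for dose changes above 20% and close examination of such cases.

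Section 1.1 says when the nudge appears, for all three patient categories: "At the time of opioid prescribing, clinicians will be prompted with an EHR nudge". Section 9.1 makes the order explicit for the opioid-naïve and at-risk categories ("Visit where the order is for an included opioid"). For the long-term category, section 5.2 gives a rule on dose and prescription history ("If an automated search of EHR data reveals total opioid doses are at least 50 MME per day") and mentions no current order.

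Section 7.3 states that "adverse events are defined as an abrupt discontinuation of opioids for persons whose most recent prescription exceeds" 49 morphine equivalents per day, and adds "or as reported to study staff". It also evaluates emergency department visits. It imposes no trigger or order condition.

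The introduction to section 7 says data on patients noted to have been abruptly stopped will be taken from the site EHR and reported to the DSMB. Section 7.2, headed as methods and timing, says only that safety reports go to the DSMB.

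**The concern.** The long-term nudge suggests a taper, and abrupt discontinuation is the harm the plan itself names. The one counting rule for dose changes that the plan spells out depends on the nudge having fired, and the nudge depends on prescribing. Some ways of stopping a patient involve no prescribing at all, so they leave no triggered visit to count.

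The study has a single arm, with no randomization, and the nudges are meant for a later cluster randomized trial. If the DSMB relied on the 7.1 count, a low figure could reflect the way cases were selected rather than an absence of harm. With no baseline figure on the same footing, the DSMB could not judge whether abrupt stops had risen.

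**Working it through.** The plan gives no adverse event rate or expected count to reproduce. The check sets sections 1.1, 5.2, 7.1 and 7.3 side by side for each way a high-dose patient can be cut or stopped. The last column assumes that the most recent prescription exceeded 49 MME/day and that the stop counts as abrupt.

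| Situation | Nudge fires? | In 7.1 count? | 7.3 event? |
|---|---|---|---|
| A. Order written at a lower dose, trigger still met | Yes | Yes, if the change exceeds 20% | No, not a discontinuation |
| B. Order opened, nudge fires, order then removed | Yes | Yes | Yes, if no opioid follows |
| C. Visit takes place, no opioid order opened | No, by section 1.1 | No | Yes |
| D. Prescription lapses, no visit | No | No | Yes |
| E. Patient fits no nudge category and is stopped by any route | No | No | Yes |

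**Row E.** Take one prior prescription 60 days ago and one 120 days ago. The patient is not opioid-naïve, because there is a prescription within 90 days. The patient is not at-risk, because there is one older than 90 days. The patient is not a long-term recipient, because that category needs two start dates within the last 90 days. No nudge fires even when an order is written, yet the patient may be above 49 MME/day.

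**Size.** Let f be the share of abrupt stops that occur through C, D or E. The 7.1 count then captures at most 1 − f of them. At f = 0 that is 100%; at f = 1 it is 0%. The documents give nothing that narrows f.

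**Baseline.** Section 3 gives 34 baseline weeks and 34 intervention weeks. With no nudge in the baseline, triggered visits there number 0 by construction. The section 6.1 schedule shows ordering data at baseline and continuously, so a search that does not depend on the nudge could be run in both periods. The same schedule marks adverse events only from the start of the intervention, under visit-level assessments.

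**Dose basis.** Section 5.2 uses total dose; section 7.3 uses the most recent prescription. As an illustration, two opioids at 40 MME/day each give 40 + 40 = 80, which meets the dose part of the long-term trigger (at least 50). Each prescription alone is 40, which does not exceed 49. If both are stopped, the 7.3 threshold is not met. Section 7.1 does not define a high-dose patient.

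**The case against.** A reader might infer that stopped patients are missed by the safety plan as a whole. The documents do not support that. The extraction in section 7 has no trigger condition, section 7.3 adds reports to staff and emergency department visits, and the 6.1 schedule marks adverse events as continuously monitored. Nothing says the 7.1 count is how 7.3 events are ascertained. This stands, and it confines the point to the 7.1 count. What it leaves open is method: the plan does not say who notes a stopped patient, from what denominator, or after what gap without a prescription.

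A reader might also infer that larger reductions are less likely to be counted. That fails on row B. In the workflow section 5.2 describes for the opioid-naïve category, and carries over to at-risk patients, "The clinician can either remove or continue with the current opioid prescription" after the alert. Removal is a 100% reduction at a triggered visit, so it is counted. A cut that takes a patient below the 50 MME/day trigger would escape only if total dose includes the current order, which the documents do not settle.

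Three further objections have some force:

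- The 7.1 sentence has no main verb. It could be read as two items: triggered visits and, separately, dose changes in high-dose patients. The restricted reading is the natural one, but it is not certain.
- Section 7.1 sets no time window. A later stop could be attributed to an earlier triggered visit, which would recover some of C and D in patients already nudged. It would not recover patients who were never nudged.
- For the long-term category, the order requirement rests on section 1.1 alone.

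Each of these is an ambiguity for the sponsor to resolve. None supplies a way of finding the patients in rows C to E.

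**Conclusion.** The point holds for the section 7.1 count. As naturally read, that count cannot include abrupt stops made without an order or without a visit, nor any stop in a high-dose patient outside the three categories, and it has no baseline comparator. Other sections cover these patients in intention but give no means of identifying them. The undercount in 7.1 is therefore of unknown size, between 0 and 100% of abrupt stops, and no figure can be given for the safety plan as a whole.

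The conclusion rests on three assumptions: that the 7.1 sentence describes one count restricted to triggered visits; that section 1.1 governs the long-term nudge as well as the other two; and that a dose change is counted at the visit where it occurs. The category gap in row E and the missing baseline do not depend on the second or third. The mismatch between total dose and most recent prescription is separate and depends on none of them.

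**What to change.** In section 7.1, base ascertainment on a patient-level search of the ordering data listed in section 6.1:

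- **Population:** every non-cancer adult of a study clinician who meets the plan's dose threshold, whether or not a nudge fired.
- **Comparison:** dose before against dose after the qualifying prescription, with no further order counted as a change.
- **Periods:** the same search in the 34 baseline weeks and the 34 intervention weeks.
- **Reporting:** all cases to the DSMB, with triggered visits as a subset.
- **Method:** section 7.2 to state the gap that defines discontinuation, the look-back and the timing of each search, and to say how this relates to the extraction in section 7.

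The sponsor must also reconcile the dose basis across sections 5.2, 7.1 and 7.3, and state whether the long-term trigger requires a current order. Which basis or threshold applies is for the sponsor to decide.

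The cost is a wording change and a different query. The extract must contain orders outside triggered visits, which should be confirmed because qualifying visits are undefined and the schedule is visit-level. There will be more cases to review, some of them patients who transferred care or stopped for other reasons.
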